7.3.3.3 Variables

The following variables will be collected for each AE:

- AE diagnosis/description
- The date the AE started and stopped
- CTCAE version 4.0 grade
- Whether the AE is serious or not and the reason(s) it is serious
- Investigator causality rating against the investigational product (yes or no)
- Action taken with regard to study treatment
- Outcome

For SAEs other variables will be collected including treatment given for the event.

It is important to distinguish between serious and severe AEs. Severity is a measure of intensity whereas seriousness is defined by the criteria in Section 7.3.2. An AE of severe intensity need not necessarily be considered serious. For example, nausea that persists for several hours may be considered severe nausea, but not a SAE. On the other hand, a stroke that results in only a limited degree of disability may be considered a mild stroke but would be a SAE.

The grading scales found in the current National Cancer Institute CTCAE version 4.0 will be utilized for all events with an assigned CTCAE grading. For those events without assigned CTCAE grades, the recommendation in the CTCAE criteria that converts mild, moderate, and severe events into CTCAE grades should be used. A copy of the current CTCAE version can be downloaded from the Cancer Therapy Evaluation Program website (<http://ctep.cancer.gov>).

7.3.3.4 Causality Collection

The Investigator will assess causal relationship between investigational product and each AE, and answer ‘yes’ or ‘no’ to the question: ‘Do you consider that there is a reasonable possibility that the event may have been caused by the study treatment?’

For SAEs causal relationship will also be assessed for other medication and study procedure(s).

A guide to the interpretation of the causality question is found in Appendix III of this Clinical Study Protocol.

7.3.3.5 Adverse Events based on Signs and Symptoms

All AEs spontaneously reported by the patient or reported in response to the open-ended and non-leading verbal questioning from the study personnel (e.g., “*How are you feeling?*” “*Have you had any health problems since the previous visit/you were last asked?*”), or revealed by observation will be collected and recorded in the eCRF. Where possible a diagnosis should be recorded, rather than recording a list of signs and symptoms. However, if a diagnosis is known and there are other signs or symptoms that are not generally part of the diagnosis, the diagnosis and each sign or symptom will be recorded separately.

7.3.3.6 Adverse Events based on Examinations and Tests

The results from protocol mandated laboratory tests, vital signs, ECGs and other safety assessments will be summarized in the Clinical Study Report. Deterioration as compared to pre-treatment in these parameters will therefore only be reported as AEs if they fulfill any of the criteria for a SAE or are the reason for modifying the study treatment unless clearly due to progression of disease under study (see Section 7.3.3.8).

If deterioration in a laboratory value, vital sign, ECG, or other safety assessment is associated with clinical events, the clinical event will be reported as an AE and the associated laboratory result or other finding will be considered as additional information. Wherever possible the reporting Investigator will use the clinical, rather than the laboratory term (e.g., anemia versus low hemoglobin value). In the absence of clinical events, clinically relevant deteriorations in non-mandated parameters should be reported as AE(s).

Deterioration of a laboratory value that is unequivocally due to disease progression should not be reported as an AE.

Any new or aggravated clinically relevant abnormal medical finding at a physical examination as compared with the pre-treatment assessment will be reported as an AE.

7.3.3.7 Hy's Law

Cases where a patient shows elevations in liver biochemistry may require further evaluation and occurrences of AST or ALT elevations in liver biochemistry that may require further evaluation

should be reported as SAEs. Please refer to Appendix IV for further instruction on cases of increases in liver biochemistry and evaluation of Hy's Law.

7.3.3.8 Disease Progression

Disease progression can be considered as a worsening of a patient's condition attributable to the disease for which the investigational product is being studied. It may be an increase in the severity of the disease under study and/or increases in the symptoms of the disease. The development of new, or progression of existing metastasis to the primary cancer under study should be considered as disease progression and not an AE. **Events that are unequivocally due to disease progression should not be reported as AEs during the study.**

7.3.3.9 New Cancers

The development of a new cancer should be regarded as an AE and will generally meet at least one of the serious criteria. New cancers are those that are not the primary reason for the administration of the study treatment and have been identified after the patient's inclusion in this study. They do not include metastases of the original cancer.

7.3.3.10 Handling of Deaths

All deaths that occur during the study, or within the 30-day follow-up period after the administration of the last dose of investigational product, should be reported as follows:

- Death, which is unequivocally due to disease progression, should be communicated to the study monitor at the next monitoring visit and should be documented in the eCRF module, but should not be reported as a SAE during the study.
- Where death is not clearly due to disease progression of the disease under study the AE causing the death should be reported to the Theradex® Safety Desk as an SAE within 24 hours. The report should contain a comment regarding the co-involvement of progression of disease, if appropriate, and should assign a single primary cause of death together with any contributory causes.
- Deaths with an unknown cause should always be reported as a SAE but every effort should be made to establish a cause of death. A post-mortem may be helpful in the assessment of the cause of death, and if performed a copy of the post-mortem results (with translation of important parts into English) should be reported in an expedited fashion to the Theradex® Safety Desk within the usual timeframes.

7.3.4 Reporting of Serious Adverse Events

All SAEs have to be reported to the Theradex® Safety Desk, whether or not considered causally related to the investigational product, or to the study procedure(s). All SAEs will be recorded in the eCRF.

If any SAE occurs in the course of the study (from signing of informed consent up to 30 days after last dose), then Investigators or other site personnel must inform the Theradex® Safety Desk

immediately, or **no later than 24 hours** of when he or she becomes aware of it.

For fatal or life-threatening adverse events where important or relevant information is missing, active follow-up is undertaken immediately. Investigators or other site personnel must inform the Theradex® Safety Desk of any follow-up information on a previously reported SAE immediately, or **no later than 24 hours** of when he or she becomes aware of it.

All SAEs require that a Serious Adverse Event Report Form be completed and forwarded either via fax or as a PDF via email to the Theradex® Safety Desk at the fax number or email listed below within 24 hours of becoming aware of the event. The fax and telephone numbers listed below may be used during both business and non-business hours. During non-business hours a recorded message will provide the caller with the contact information for the on-call monitor.

EU and US sites will report SAEs to:	Theradex® (Europe) Ltd. Safety Desk REDACTED
--------------------------------------	--

7.4 Pregnancy

All pregnancies and their subsequent outcome (spontaneous miscarriage, elective termination, ectopic pregnancy, normal birth or congenital abnormality) should be reported to the Theradex® Safety Desk using the appropriate forms.

7.4.1 Maternal Exposure

If a patient becomes pregnant during the course of the study investigational product should be discontinued immediately.

Pregnancy itself is not regarded as an adverse event unless there is a suspicion that the investigational product under study may have interfered with the effectiveness of a contraceptive medication. Congenital abnormalities/birth defects and spontaneous miscarriages should be reported and handled as SAEs. Elective abortions without complications should not be handled as AEs. The outcome of a pregnancy should be followed up and documented even if the patient was withdrawn from the study.

If a pregnancy occurs during exposure to investigational product or in the 30 days after discontinuing investigational product, then Investigators or other site personnel must inform the Theradex® Safety Desk immediately, or **no later than 24 hours** of when he or she becomes aware of it.

The same timelines apply when outcome information is available.

8.0 EFFICACY ASSESSMENTS

Patients with measurable disease will be assessed by standard criteria.

For patients in Arm A or Arm B: A CT scan/MRI should be performed at pre-treatment (within 4 weeks prior to day 1 of study treatment) and at the end of cycle 2 (within 7 days prior to the start of cycle 3), and at the end of cycle 4 (within 7 days prior to the start of cycle 5), and after the last cycle. At subsequent follow-up visits, tumor assessments by CT scan/MRI will be performed 2 months (\pm 2 weeks) after the end of treatment visit and every 3 months (\pm 2 weeks) thereafter, until the documented disease progression, as determined by the Investigator at each site and defined by RECIST v1.1.

Central reading for all scans will be performed during the study. After CT/MRI acquisition, the exam will be transferred for central reading by two expert readers (see Radiology Manual for further details). The central reader will visualize the image in order to evaluate the clinical response based on RECIST v1.1 criteria. The central review will be performed in batches throughout the study. Treatment decisions should be based upon results of the local review.

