Study Design: This study is an open-label, randomized, multi-center Phase II proof-of-concept study with a dose confirmation component (dose confirmation component now completed) to assess whether patients with platinum sensitive recurrent p53 mutated high grade serous ovarian cancer (HGSOC) will benefit from treatment with APR-246 in combination with a carboplatin/pegylated liposomal doxorubicin (PLD) chemotherapy regimen. All patients will have pre-screening immunohistochemistry (IHC) test that will determine p53 status and therefore the suitability to participate in this study. Patient's archived sections from the original tumor sample will be reviewed by a gynecological pathologist to confirm the diagnosis of HGSOC, and positive staining for p53. Patients without positive p53 staining will not be included. Patients will be randomly assigned in a 1:1 ratio to receive either: 
• Arm A: APR-246 with the carboplatin/PLD chemotherapy regimen,• Arm B: Carboplatin/PLD chemotherapy alone. The trial will enroll up to a maximum of 400 patients with positive IHC staining for p53. A CT scan/MRI using RECIST v1.1 criteria will be performed at pre-treatment, after 2 cycles (8 weeks), 4 cycles (16 weeks), and after the last cycle (24 weeks).	

At subsequent follow-up visits, tumor assessments by CT scan/MRI will be performed 2 months (\pm 2 weeks) after the end of treatment visit and every 3 months (\pm 2 weeks) thereafter, until the documented disease progression, as determined by the Investigator at each site and defined by RECIST v1.1.

Optional frozen/fixed core biopsies will be undertaken after randomization, but prior to any infusion, for all patients and on day 3 in APR-246 patients.

Objectives, Endpoints and Study Treatment:

Objectives:

Primary Objective:

- To assess the efficacy of a combined APR-246 and carboplatin/PLD chemotherapy regimen in patients with platinum sensitive recurrent HGSOC with mutated TP53.

Secondary Objective:

- To assess the safety profile of the combined APR-246 and carboplatin/PLD chemotherapy regimen compared with carboplatin/PLD chemotherapy regimen alone.
- To evaluate potential biomarkers.
- To assess the biological activity in tumor and surrogate tissues.
- To compare quality of life of patients treated with these regimens.

Endpoints:

Primary Endpoint

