4.0 STUDY DESIGN

4.1 Overview of Study Design

This study is an open-label, multi-center Phase II proof-of-concept study with a dose confirmation component to assess whether patients with platinum sensitive recurrent TP53 mutated high grade serous ovarian cancer (HGSOC) will benefit from treatment with APR-246 in combination with a carboplatin/PLD chemotherapy regimen. It is planned that patients will receive up to 6 cycles of treatment.

Archived sections from the original tumor sample will be reviewed by a gynecological pathologist to confirm the diagnosis of HGSOC and positive IHC staining for p53 (please refer to the laboratory manual). Patients without positive p53 staining will not be included.

Patients will be randomly assigned in a 1:1 ratio to receive either:

- Arm A: APR-246 with the carboplatin/PLD chemotherapy regimen,
- Arm B: Carboplatin/PLD chemotherapy alone.

Optional frozen/fixed core biopsies will be undertaken after randomization, but prior to any infusion, on day 1 for all patients and day 3 in APR-246 patients.

The study will enroll up to 400 patients with positive IHC staining for p53. A CT scan/MRI using RECIST v1.1 criteria will be performed at pre-treatment, after 2 cycles (8 weeks), 4 cycles (16 weeks) and after the last cycle (24 weeks).

At subsequent follow-up visits, tumor assessments by CT scan/MRI will be performed 2 months (\pm 2 weeks) after the end of treatment visit and every 3 months (\pm 2 weeks) thereafter, until the documented disease progression, as determined by the Investigator at each site and defined by RECIST v1.1.

All scans for each individual patient should have the same modality (CT or MRI) but CT is preferred.

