6.4 Treatment Administration

6.4.1 Treatment Arm A: APR-246 with carboplatin and PLD

Patients will receive a fixed dose of 4.5 g APR-246 (1.5 g of the dose during first 45 minutes followed by 3 g of the dose during 5 hours 15 minutes) on Days 1 to 4 with carboplatin AUC 5 and PLD 30 mg/m² on Day 4 (Figure 3). Carboplatin and PLD administration to be given on Day 4 only should commence 2 hours after the start of the APR-246 infusion. Further administration of APR-246 (repeated in 28-day cycles) will commence three days prior to subsequent chemotherapy cycles, with the fourth dose administered the same day as the chemotherapy.

[figure not shown]

Figure 3. Treatment Administration for Patients Receiving APR-246

Note: The entire dose should be given even if the infusion needs to be extended beyond a total time of 6 hours (e.g. due to slightly larger start volume in prefilled infusion bags).

APR-246 Treatment Duration

Treatment will be repeated every 28 days for up to 6 cycles in the absence of disease progression or unacceptable toxicity. Supportive therapy, including growth factors, can be given as per institutional standard of care.

Carboplatin Dosing

The dose of carboplatin will be calculated as per standard practice at that hospital. Patients will start at carboplatin with an AUC 5.

Pegylated Liposomal Doxorubicin Dosing

The dose of PLD will be calculated based on the body surface of the patients at 30 mg/m^2 as per standard practice at that hospital.

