6.5.1.1 APR-246 Infusion and Systemic Chemotherapy Delays

The days 1 to 4 APR-246 administration, together with the day 4 chemotherapy, are to be regarded as one treatment cycle and must be administered consecutively.

On day 1, prior to APR-246 administration, the hematological status of the patient should be assessed. If the patient has any hematological adverse event that would prevent systemic chemotherapy administration on day 4, the APR-246 infusion and systemic chemotherapy should be delayed until recovery (see Section 6.5.2.1).

If a patient has any adverse event on days 2, 3 or 4 prior to the APR-246 infusion which, in the opinion of the Investigator, would prevent systemic chemotherapy administration, the remainder of the planned APR-246 administration should be stopped. Once the patient has recovered sufficiently to receive chemotherapy, the whole treatment cycle (consisting of days 1-4 APR-246 and day 4 chemotherapy) should be restarted as previously planned.

If APR-246 and/or systemic chemotherapy are delayed, the reasons for delay should be recorded in eCRF.

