6.5.2.1 Hematological Toxicity and Dose Modifications

The absolute neutrophil count (ANC) must be $\geq 1.50 \times 10^9/L$ and the platelet count must be $\geq 100 \times 10^9/L$ in order to administer full doses of carboplatin and PLD in each cycle as assessed on day 1. In the event of an $ANC < 1.0 \times 10^9/L$, hematological assessment should be performed twice a week until recovery of ANC to $> 1.0 \times 10^9/L$. Patients should be monitored prior to each dose for platelet and neutrophil counts, and at the discretion of the Investigator, if necessary, the dose of carboplatin and/or PLD may be either reduced or withheld in the presence of hematological toxicity according to the following scale (Table 3):

Table 3. Dose Modification of Systemic Chemotherapy for Hematological Toxicities

Hematological Assessment on Day 1 of a Cycle:			
ANC ($\times 10^9/L$)		Platelet Count ($\times 10^9/L$)	Dose Modification
≥ 1.5	and	≥ 100	Administer full dose of Carboplatin and PLD
< 1.5	and/or	< 100	Delay cycle for 7 days. If within normal acceptable parameters (as above) proceed with dose reductions of carboplatin to AUC 4 and PLD 25 mg/m ² .
Dose reduction to carboplatin AUC 4 and PLD 25 mg/m ² is also required in the following circumstances:			

• $ANC < 0.5 \times 10^9/L$ for > 7 days• An episode of febrile neutropenia (temp $\geq 38.5^\circ C$ and $ANC < 1.0 \times 10^9/L$)• Platelets $< 25 \times 10^9/L$, or bleeding requiring a platelet transfusion			

Growth factors:

- For patients who have a prolonged neutropenia, Investigators may administer growth factors to aid white cell count recovery. This should be given per the package insert.
- Patients who the Investigator considers to be at risk for developing neutropenia (considering bone marrow tolerance with prior chemotherapy or neutropenia while on the PiSARRO study)

that could affect their ability to receive study treatment per the study protocol, should consider administering prophylactic growth factor per the package insert.

For patients in Arm A:

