13. EoT visit should take place 7 days after the completion of 6 cycles of chemotherapy (between day 28 and day 35 of cycle 6) or up to 30 ± 2 days after the last administration of APR-246 if treatment is stopped early for any reasons.
14. The first follow-up visit should commence 2 months (± 2 weeks) after the EoT visit. Subsequent follow-up visits should be performed every 3 months (± 2 weeks) until documented disease progression as defined by RECIST v1.1.

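### Scans follow actual cycle starts and the EoT visit, so unequal cycle delay between arms shifts PFS dates; Arm B's early-stop EoT visit is dated from a drug it never receives

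*Combined protocol and SAP*

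**What the plan says.** **Scan times.** The synopsis places CT or MRI "after 2 cycles (8 weeks), 4 cycles (16 weeks), and after the last cycle (24 weeks"), and section 4.1 has the same ("after 2 cycles (8 weeks), 4 cycles (16 weeks) and after the last cycle (24 weeks"). Section 8.0, section 7.2.4 and footnote 2 of Tables 9 and 10 make the rule operational. The first on-treatment scan is "at the end of cycle 2 (within 7 days prior to the start of cycle 3"), the second stands in the same relation to cycle 5, and the third follows the last cycle. Under 7.2.6 the follow-up scans are counted from the EoT visit: two months after it, then at three-month intervals, each with a two-week window. After six cycles, the EoT visit is itself tied to days 28 to 35 of cycle 6 (7.2.5).

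**Endpoint and test.** PFS runs from randomization to objective progression or death (3.1.3, 9.1). The final stratified logrank test uses one-sided 0.023 (9.5.2.1), and 9.8.4 puts Type I error below 0.025. Section 9.5.2 names no analysis that deals with scan timing.

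**Sources of delay.** Counts must meet the thresholds "in order to administer full doses of carboplatin and PLD in each cycle as assessed on day 1". If they do not, Table 3 says "Delay cycle for 7 days". In Arm A, 6.4.1 has "Carboplatin and PLD administration to be given on Day 4 only"; in Arm B chemotherapy is on Day 1. Section 6.5.1.1 concerns Arm A only: after an adverse event on days 2 to 4 that rules out chemotherapy, "the whole treatment cycle (consisting of days 1-4 APR-246 and day 4 chemotherapy) should be restarted as previously planned".

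**EoT after an early stop.** Footnote 13 of Table 10, the Arm B schedule, and section 7.2.5 place this visit up to 30 ± 2 "days after the last administration of APR-246 if treatment is stopped early for any reasons". Section 6.4.2 says that Arm B gets no APR-246.

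**The concern.** The week numbers and the cycle anchors agree only if no cycle is delayed. Once a cycle slips, every later scan in that patient slips too, while the PFS clock still starts at randomization. Progression is dated at the scan that shows it, so a later scan means a longer recorded PFS whatever the drug does. Blinded central review re-reads the images but cannot change when they were taken.

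Equal delay in the two arms does no harm to the comparison. Unequal delay does, and two features make more delay in Arm A plausible: the whole-cycle restart exists only there, and its gating counts are taken sooner after chemotherapy. At stake is the error rate of a test whose nominal level (0.023) lies only 0.002 below the limit the plan claims (0.025), in an open-label design meant to be able to support conditional approval (9.3).

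The EoT anchor is a separate defect. Table 10 does mark an EoT scan for Arm B, but for an Arm B patient who stops early neither the EoT date nor the follow-up scans counted from it are defined.

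**Working it through.** **1. The plan's weeks.** Week = cycles × 28 / 7. For 2, 4 and 6 cycles this gives 8, 16 and 24, as stated.

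**2. What delay does to them** (7-day step, Table 3).
- One delay before the scan: (56 + 7)/7 = 9, (112 + 7)/7 = 17, (168 + 7)/7 = 25.
- A delay at every start of cycles 2 to 6: (56 + 14)/7 = 10, (112 + 28)/7 = 20, (168 + 35)/7 = 29. All follow-up scans then move by 5 weeks, because they are counted from EoT.

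**3. Time from chemotherapy to the gating count.** Day 1 of the next cycle is day 29 of the current one. Arm A: 29 − 4 = 25 days. Arm B: 29 − 1 = 28 days.

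**4. Null simulation (HR 1).**
- From the documents: one-sided 0.023; maximum N 400, 1:1; cut-off 12 months after the last enrolment; looks at 150, 200, 250, 300 and 350; small-effect stop if Pr(HR < 0.8) < 0.30; success stop if PPoS > 0.95 from 200; prior N(0, 0.5²) on the log HR; 7-day delays. The 11.3-month median is the figure in 2.2 for this regimen, not a stated design input.
- Assumed: delay probability per cycle (cycles 2 to 6) by arm, accrual rate, and randomization as cycle 1 Day 1.
- Model: exponential progression, rate ln 2 / median, dated at the next scan. Scans fall 0 to 7 days before days 56 and 112 plus accumulated delay, 0 to 7 days after the end of cycle 6, then at EoT + 61 days and every 91 days, each ± 14 days. Censoring is at the last scan. The logrank test is tie-corrected and unstratified, with no strata effects simulated. The posterior and PPoS use normal approximations, without the CA-125 model.
- 20,000 trials per row, standard error about 0.001.

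| One-week delay per cycle, Arm A vs Arm B | Fixed N = 400 | Adaptive, small-effect stop counts as failure | Adaptive, final test still run after such a stop |
|---|---|---|---|
| Fixed-week scans (control) | 0.0245 | 0.014 | 0.018 |
| 20% vs 20% (control) | 0.024 | 0.015 | 0.020 |
| 20% vs 10% | 0.033 | 0.021 | 0.026 |
| 30% vs 10% | 0.038 | 0.026 | 0.029 |
| 50% vs 10% | 0.050 | 0.037 | 0.041 |
| 10% vs 30% (reverse) | 0.012 | 0.006 | 0.009 |

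The last column matters because 9.8.3.2 lets the sponsor continue blinded follow-up after a small-effect stop.

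**5. Ranges at 30% vs 10%** (same column order).
- Median 9.4 months: 0.041 / 0.030 / 0.034.
- Accrual 8 or 25 per month: 0.038–0.041 / 0.028–0.029 / 0.031–0.034.
- 10% of events exactly dated deaths: 0.036 / 0.025 / 0.029.

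**6. Not monotone.** Every Arm A cycle 7 days late: 0.043 / 0.030 / 0.036. Every Arm A cycle 14 days late: 0.012 / 0.007 / 0.009. With enough delay the two arms' scan times come partly back into alignment.

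**7. Is the anchoring the cause?** In a separately coded run (3,000 trials per scenario, medians 9.4 and 11.3 months, fixed N), Arm A had 50% delays and Arm B none. Cycle-tied scans gave 0.061–0.066 with mean HR 0.95. Fixed-week scans with the same delays gave 0.022–0.023 with mean HR 1.00. At a true HR of 0.70, cycle-tied scans moved the mean estimate to 0.66.

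**8. Repeatability.** Further separate codings of the three main rows at fixed N gave 0.030–0.033, 0.037–0.039 and 0.049–0.052. One of them also ran the adaptive rules: 0.019 / 0.024, 0.027 / 0.031 and 0.037 / 0.043, with fixed-week controls of 0.010 / 0.014.

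**9. EoT anchor alone**, with 20% early stoppers assumed: 0.023 / 0.013–0.014 / 0.017, so no inflation.

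**The case against.** The strongest reply is that the cycle is the anchor throughout, the weeks in parentheses are only its nominal equivalent, and the rule is identical in both arms. That is a fair reading, and it makes this a design choice more than a contradiction. It does not remove the mechanism.

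Second, the documents give no delay rates by arm. Growth factors are allowed and doses are reduced after a delay, which should limit repeat delays, whereas the simulation uses a constant, independent probability. This stands: neither the direction nor the size of the imbalance is established.

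Third, the stated limit describes the adaptive design, so the fixed-N column is not the plan's own error rate. This also stands. In the mildest row the adaptive figures (0.021 and 0.026; 0.019 and 0.024 in the repeat) do not clearly exceed 0.025. At 30% vs 10% with small-effect stops as failures, the excess is about one standard error. Clear excess needs 30% vs 10% with the final test still run, or 50% vs 10%. The sponsor's own simulations, in Appendix V, are redacted and could not be compared.

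Fourth, the model leaves out a gap between randomization and Day 1, and scans prompted by CA-125 (7.2.6). Fixed-N reruns with assumed values for the 20, 30 and 50% vs 10% rows (standard error about 0.002) gave:
- 0–14 day gap: 0.028, 0.036, 0.047.
- 30% of progressions found off schedule within 28 days: 0.028, 0.030, 0.035.
- Both, plus confirmatory scans in 60%: 0.027, 0.031, 0.033.

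The inflation shrinks but remains. The adaptive versions were not rerun with these features.

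**Conclusion.** Both parts hold. Tying scans to actual cycle starts and EoT opens a route by which unequal delay alone biases the primary PFS comparison. If Arm A is delayed more by one-week steps, at 20 to 50% of cycles against 10%, the one-sided error is 0.033 to 0.050 at a fixed 400 patients and 0.021 to 0.041 under the adaptive rules. The matching fixed-week figures are 0.0245 and 0.014 to 0.018. If Arm B is delayed more, the test is conservative; if delays are equal, there is no bias.

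The mechanism and the remedy are firm. The size is only moderately certain, because it rests on assumed delay rates, accrual and scan behavior. The change is worth making; the point does not by itself invalidate the design.

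The Arm B EoT date is a plain contradiction and needs no simulation. It does not raise Type I error, but sites have no rule for when Arm B early stoppers are scanned.

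**What to change.** - In 8.0, 7.2.4 to 7.2.6 and footnote 2 of Tables 9 and 10, schedule tumor assessments in both arms at weeks 8, 16 and 24 from randomization. After that use fixed weeks that match the present follow-up spacing, regardless of cycle delay or discontinuation.
- In the same edit, state visit windows, allow for the gap between randomization and Day 1, and re-anchor the confirmatory scans and the quality-of-life questionnaires that are tied to imaging.
- In the EoT footnotes (14 in Table 9, 13 in Table 10) and in 7.2.5, replace the APR-246 anchor with the last dose of study treatment, the reference point 7.3.3.1 already uses for adverse events. Word the early-stop EoT scan so that it covers Arm B.
- Report actual scan times and cycle delay by arm.
- Add a sensitivity analysis that assigns progression to the scheduled visit, but not in place of fixed scans. With cycle-tied scans it over-corrects: at fixed N it gives 0.021, 0.017 and 0.011 in the three main rows and 0.029 in the reverse row.

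The cost is amendment wording. The number of planned scans is unchanged, but when a cycle is delayed some scans will not coincide with a cycle visit.
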